7.1.3 Follow-up Period (Days 6 to 14)

Study Site Visits (Days 9 and 14):

Subjects should return to the study site for follow-up visits on Day 9 and Day 14 (EOS Visit) for post-treatment safety assessments. Visit assessments may be completed at the study site or by a study nurse via a home visit, if feasible; refer to the SPM for details.

Subjects who discontinue the study early (ie, prior to Day 14) should return to the study site within 24 hours and no more than 48 hours later to complete the EOS procedures.

All study assessments during the Follow-up Period are detailed in the SoA ([Appendix 1](#)).

Throughout the study, safety for each subject in each study period will be evaluated by assessment of clinical laboratory findings, physical examination findings (as applicable), vital sign measurements, pulse oximetry measurements (only for subjects with asthma or COPD), and AEs. Any subject with ongoing AEs/SAEs at the EOS Visit should be followed up until resolution of their AE/SAE or until the Investigator has determined that the event has stabilized as discussed in [Section 9.3](#).

7.2 Subject Withdrawal/Early Termination

Subjects may withdraw from the study at any time at their own request, or subjects may be withdrawn at any time at the discretion of the Investigator or Enanta Pharmaceuticals, Inc. for safety, behavioral, or administrative reasons. However, the Investigator should consult with the [REDACTED] Medical Monitor where possible before prematurely removing a subject. For any subject who decides to withdraw from the study, the Investigator should inquire about the reason for withdrawal, request that the subject returns all unused investigational product(s), request that the subject returns for a final study site visit, if applicable, and follow up with the subject regarding any unresolved AEs. Although a subject may discontinue the study drug or the study early, every effort must be made for the subject to return to the site within 24 hours and no more than 48 hours later to complete the EOS procedures.

If a subject withdraws from the study and also withdraws consent for disclosure of future information, no further evaluations should be performed, and no additional data should be collected. Enanta Pharmaceuticals, Inc. may retain and continue to use any data collected before such withdrawal of consent.

Any randomized subjects who withdraw or are withdrawn from the study will not be replaced.

7.2.1 Withdrawal Criteria

Subjects may be discontinued from the study at any time if the subject, Investigator, or Sponsor determines that it is not in the best interest of the subject to continue participation. Reasons for discontinuation include the following:

- AE
- Lack of efficacy
- Lost to follow-up
- Withdrawal by subject
- Protocol deviation (including noncompliance with study drug or study procedures)
- Pregnancy
- Study terminated by the Sponsor
- Other

7.2.2 Procedures for Early Discontinuation or Early Termination of Treatment

Subjects who prematurely discontinue treatment early and have received at least one dose of study drug should return to the site within 24 hours and no more than 48 hours later and undergo the EOS procedures per the SoA ([Appendix 1](#)). Any subject who withdraws with ongoing AEs/SAEs should be followed up until resolution of their AE(s) or until the Investigator has determined that the AE(s) has stabilized.

Site staff will attempt to contact any subject who does not return to the site for the EOS Visit at least three times using the subject's preferred method of communication, followed by a letter requiring delivery notification if the three attempts were unsuccessful. Any subject who still cannot be reached following those attempts will be considered lost to follow-up. These subjects will be included in the PK and safety analysis as indicated in [Section 11.3](#).

7.2.3 Documentation of Withdrawal of Subjects

The reason for early withdrawal/termination/lost to follow-up of any subject from the study must be documented on the appropriate eCRF. If the reason for early withdrawal is an AE or an abnormal laboratory value, the specific event or test result, if available, should be recorded on the AE eCRF and the subject should be monitored until the event is resolved or deemed stable by the Investigator.

8. STUDY PROCEDURES/EVALUATIONS

8.1 Timing of Assessments

The timing of assessments is shown in the SoA ([Appendix 1](#)).

8.2 Demographics and Medical History

Demographics and baseline characteristics including date of birth or age, gender or sex, race, ethnicity, medical history, and smoking history will be obtained from each subject and entered in the eCRF as reported during Screening. Significant medical history will be obtained by consulting with the subject. As a general rule, all medical events occurring within the last 6 months should be recorded. For events that occurred more than 6 months ago (and that are not ongoing), only significant or relevant events should be entered on the eCRF. Any items in the history that are still ongoing should be noted as such in the eCRF. All surgeries occurring in adulthood should be recorded in the eCRF, whereas surgical methods of contraception, if applicable, should only be documented in the source documents.

If there is a question concerning a subject's medical history, then medical records may be requested from the subject's primary care physician, as appropriate.

8.2.1 Prior and Concomitant Medications

Any medication taken during the course of the study through the end of the study will be recorded with indication, dosage, route of administration, and start and stop dates of administration. All subjects will be questioned about concomitant medication at each study site visit.

8.3 Clinical Evaluations

8.3.1 Vital Sign Measurements

Vital signs include heart rate, respiratory rate, systolic and diastolic blood pressure, and body temperature. Vital signs will be measured at times shown in the SoA ([Appendix 1](#)) after the subject has been supine for a minimum of 5 minutes.

8.3.2 Electrocardiograms

A resting 12-lead ECG will be performed locally and recorded at Screening on Day 1 as specified in the SoA ([Appendix 1](#)) after the subject has been supine for 5 minutes and before dosing. A standard bedside 12-lead ECG machine that calculates heart rate and measures PR, QRS, QT, RR, and QTcF intervals will be utilized.

At Screening on Day 1, the Investigator or designee should review the ECG for gross abnormalities and interval measurements of concern (absolute readings). The clinical interpretation by the Investigator or designee of the ECGs should be recorded on a hard copy of the ECG (ie, clinically significant or not clinically significant).

An ECG may be repeated at the discretion of the Investigator to address suspected errors in performance. Prior to dosing, the screening ECG must be reviewed to confirm that no clinically significant cardiac abnormalities are present.

8.3.3 Physical Examination

The Investigator or designee will perform the physical examination. A full physical examination will be conducted at Screening and will include examination of all pertinent body systems. Any subsequent physical examinations performed at the discretion of the Investigator will be targeted to new signs and symptoms including specific assessments of any changes from previous status. Only clinically significant abnormalities should be recorded in the eCRF (eg, use of contact lenses does not need to be recorded).

8.3.4 Height, Weight, and Body Mass Index

Height and body weight should be obtained with the subject in light clothes and no shoes. Height will be documented at Screening only. Body mass index will be calculated at Screening (to assess eligibility) according to the following equation:

$$\text{BMI} = \text{weight (kg)} / \text{height (m)}^2$$

These measurements will be obtained as specified in the SoA ([Appendix 1](#)).

8.3.5 Adverse Events

The Investigator is responsible for the detection and documentation of events meeting the criteria and definition of an AE or SAE as provided in [Section 9.1](#) of this protocol. All AEs and SAEs must be recorded in the source documents and eCRF as described in [Section 9.2](#). At all study site visits, the Investigator or designee should inquire about the occurrence of AEs. The following are examples of open-ended questions that may be used to obtain this information: “How are you feeling?”; “Have you had any medical problems recently?”; and “Have you taken any new medicines since your last visit/assessment?”

It is the Investigator’s responsibility to ensure any necessary additional therapeutic measures and follow-up procedures are performed and documented in the subject source notes and eCRF.

8.3.6 Pulse Oximetry

At Screening, subjects diagnosed with asthma or COPD will have pulse oximetry performed to measure oxygen saturation and to ensure study exclusion criteria are not met (see [Section 3.2](#)).

Subsequent pulse oximetry measurements will be performed for subjects with asthma or COPD as indicated in the SoA ([Appendix 1](#)).

8.3.7 Frailty Scale Score

At Screening, all subjects will have a frailty scale score documented by the Investigator or site staff based on subject interview and medical history to ensure that study exclusion criteria are not met (see [Section 3.2](#)). Frailty will be assessed by a validated 9-point scale ([Rockwood et al., 2005](#)) or as otherwise indicated in the SPM.

8.3.8 Respiratory Syncytial Virus Symptom Diary

At Screening and at timepoints indicated in the SoA ([Appendix 1](#)), subjects will assess the severity of RSV-related signs and symptoms and self-complete the 13-point RSV symptom diary. The 13-item diary will consist of grading symptoms on a scale of 0 to 3, where Grade 0 is absence, Grade 1 is just noticeable, Grade 2 is bothersome but does not prevent participation in activities, and Grade 3 is bothersome and interferes with activities. The 13 RSV symptoms assessed will comprise nasal discharge, nasal congestion, malaise/tiredness, headache, sinus congestion, sneezing, sore throat, hoarseness, cough, shortness of breath, respiratory wheeze, earache, and/or symptoms of fever. The RSV symptom diary will be completed twice daily at the same times each day ± 2 hours as an eCOA. In case the subject is unable to complete the RSV symptom diary assessment for technical reasons, the subject will also be provided with a paper diary(ies) as a back-up. If a subject plans to take acetaminophen within 2 hours of the scheduled RSV symptom diary completion, then the RSV symptom diary should be completed immediately before the subject takes acetaminophen or 4 hours after taking acetaminophen.

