- ^l Follicle-stimulating hormone should be tested in postmenopausal females. Refer to [Section 8.4.2](#).
- ^m Clinical laboratory tests include chemistry, hematology, and urinalysis. See [Section 8.4](#) and [Table 2](#) for details regarding Day 1 sample collection and evaluations for the local and central laboratory(ies).
- ⁿ Subjects who meet all inclusion criteria and none of the exclusion criteria to the satisfaction of the Investigator, including the screening ECG and the screening urine pregnancy test, will be eligible to enter the study and will be randomized 1:1 to receive 800 mg of EDP-938 or placebo. Subject randomization will be stratified by the presence or absence of asthma/COPD.
- ^o Eligible subjects will receive an electronic data capture handheld device (ERT[®] eCOA Handheld eDiary) on Day 1 and will return the device to the study site at the EOS Visit. Refer to [Section 7.1.2](#) for additional details.
- ^p The RSV symptom diary will be self-completed by subjects twice daily at the same times each day ± 2 hours as an eCOA. If a subject plans to take acetaminophen within 2 hours of the scheduled RSV symptom diary completion, then the RSV symptom diary should be completed immediately before the subject takes acetaminophen or 4 hours after taking acetaminophen.
- ^q [REDACTED]
- ^r [REDACTED]
- ^s Study drug (EDP-938 or placebo) should be administered at the study site on Days 1 and 5. On Day 5, the study site visit should be scheduled close to the time that the subject normally takes the study drug so that dosing can occur at the site. From Day 1, subjects will electronically record the time and date that each dose is taken. See [Section 5.7](#) for additional dosing details.
- ^t Study drug accountability by tablet count and review of the electronic dosing record completed by the subjects.
- ^u On Day 1, collect one postdose plasma PK sample, at least 1 hour after dosing or right before the subject leaves the site, whichever is later. On Day 3, collect one plasma PK sample at the same approximate time as that of the NP swab collection. On Day 5, collect one predose PK sample. If the subject takes the study drug prior to the study site visit, a PK sample should be taken at the same approximate time as that of the NP swab collection. See [Section 5.7](#) and [Section 8.6](#) for additional details.

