#### 3.14.1 Primary Efficacy Analyses

The primary efficacy analysis will be performed on the total symptom score (TSS) AUC on the respiratory syncytial virus symptom diary (see Appendix 5.2) using the mITT population. The primary efficacy analysis will be repeated using the PP population. The TSS is measured twice daily using a 13-point symptom scale. Date and time of completion will be recorded. For Day 1,

the TSS is measured first pre-dose and then post-dose. Subjects have been instructed to complete the symptom scale either immediately before or 4 hours after using acetaminophen medication to avoid confounding results. From Day 1 through Day 14, subjects will electronically record the date and time of any acetaminophen use.

The TSS will be derived for each subject using the electronic data capture handheld device (ERT® electronic clinical outcome assessment [eCOA] Handheld eDiary) or paper diary. Baseline TSS will be collected once on Day 1 prior to first dose. If baseline TSS is missing, the assessment of TSS post-dose on Day 1 will be used as baseline. The average daily TSS will be computed as part of the primary efficacy endpoint analysis.

The TSS will be derived for each subject, separately for each of the two assessments on each day (Day 1 to Day 14) as follows:

- 1) For each assessment, sum the 13 observed symptom grade values for a total symptom score. If any of the 13 observed values are missing the total symptom score will not be calculated for that assessment.

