The TSS AUC from Day 1 through Day 14 will be calculated using the trapezoid rule (*Matthews et al., 1990*). The AUC will require at least 2 non-missing calculated total symptom scores. Missing total symptom score data will be reviewed for potential impact, and any decisions to include subjects that fail these criteria above will be documented. The AUC will be calculated based on available individual assessments of TSS collected twice per day from Day 1 through Day 14, and the actual date/time of each assessment will be used for the calculation. For the baseline TSS, the actual time is set as 0. For each assessment post first dose, the actual time in days is computed as difference between the date/time of the assessment and the date/time of the first dose. The AUC is also standardized for 14 days by multiplying  $14/t_{last}$  where  $t_{last}$  is the actual time in days of the last available assessment. Additionally, the AUC from Day 1 through Day 3, the AUC from Day 1 through Day 5, and the AUC from Day 1 through Day 9 will be also derived and standardized similarly as for AUC from Day 1 through Day 14.

The AUC TSS from Day 1 through Day 14 will be compared between EDP-938 and placebo using an analysis of covariance (ANCOVA) model with treatment group, asthma/COPD status (present or absent) as factors and the baseline TSS as a covariate. The analysis will be performed using SAS procedure MIXED. Treatment groups will be compared using a type III sum-of-squares. The least-squares means, standard errors and two-sided 95% confidence intervals (CI) will be presented for individual groups and the difference between groups. The same ANCOVA analysis will be performed for the TSS AUC from Day 1 through Day 3, from Day 1 through Day 5 and from Day 1 through Day 9.

Descriptive statistics will be displayed for TSS and change from baseline by day and timepoint and also for average daily TSS by day and will include at a minimum the number of non-missing measurements, mean, standard deviation, median, minimum, maximum, and 95% CI for the mean.

Multiple line graphs of TSS will be produced:

- (1) Observed mean TSS  $\pm$  95% confidence interval by days 1-14 and timepoint for each treatment group
- (2) Observed mean TSS (average per day)  $\pm$  95% confidence interval by days 1-14 for each treatment group

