### 3.14.1.1 Sensitivity Analysis of the Primary Endpoint

If acetaminophen use is within 4 hours before a TSS, then the TSS may have been impacted. Thus, TSS AUC for mITT analysis will be reproduced after excluding such TSS assessments post-baseline.

Time to resolution of TSS will be analyzed using a Cox Proportional Hazards model. This will be performed for the mITT population. Stratification factors, baseline TSS and asthma/COPD status (present or absent), will be included. Time to resolution of TSS will be defined as the time from first dose to first of two consecutive timepoints where TSS is zero (days). Consecutive timepoints is defined as two consecutive timepoints planned per protocol, e.g. Day 2 timepoint 2 and Day 3 Timepoint 1. A Kaplan-Meier curve will display the probability estimates with resolution. Descriptive statistics on the graph will include the median and 95% confidence interval at a minimum.

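### The acetaminophen rule for the symptom diary offers a 4-hour delay that almost never fits the ±2 h window, and its 2 h trigger covers only half of the 4 h interval the SAP treats as possibly affected

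*Protocol*

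**What the plan says.** **Diary timing.** Protocol 8.3.8: "The RSV symptom diary will be completed twice daily at the same times each day ± 2 hours as an eCOA".

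**Acetaminophen rule.** Protocol 8.3.8, Schedule of Assessments footnote p (in both the protocol and the SAP) and SAP 5.2 give the same conditional rule. It starts "If a subject plans to take acetaminophen within 2 hours of the scheduled RSV symptom diary completion" and continues that "the RSV symptom diary should be completed immediately before the subject takes acetaminophen or 4 hours after taking acetaminophen". I call these the before option and the delay option.

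**SAP account of the rule.** SAP 3.14.1: "Subjects have been instructed to complete the symptom scale either immediately before or 4 hours after using acetaminophen medication to avoid confounding results". The 2 h condition is absent there.

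**SAP view of contamination.** SAP 3.14.1.1: "If acetaminophen use is within 4 hours before a TSS, then the TSS may have been impacted". The consequence is confined to a sensitivity analysis: "TSS AUC for mITT analysis will be reproduced after excluding such TSS assessments post-baseline".

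**Primary analysis.** SAP 3.14.1: "The AUC will be calculated based on available individual assessments of TSS collected twice per day from Day 1 through Day 14". Actual date and time are used. Nothing is excluded because of acetaminophen or because a diary fell outside ±2 h.

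**The concern.** Acetaminophen is the only antipyretic or analgesic that Protocol 5.9 permits, and headache, sore throat, earache and fever symptoms are among the 13 diary items. SAP 5.2 itself says that the timing of acetaminophen matters because it can confound the primary analysis. The timing rules are therefore the only protection the primary endpoint has against a score taken under recent symptomatic relief.

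Two things do not fit:

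- One of the two options offered to the subject conflicts with the diary window stated in the same section.
- The rule makes the subject wait 4 h, and the SAP looks back 4 h, but the rule is triggered only within 2 h. A dose 2 to 4 h before the diary triggers no instruction, although the SAP regards the score as possibly affected.

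At stake are some possibly affected scores in the primary AUC, a sensitivity analysis that loses scores from subjects who did as they were told, and a SAP description that credits the data with more protection than the instruction gives.

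**Working it through.** The plan states no figure to reproduce here. The check is interval arithmetic on its own times.

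**Inputs.** Scheduled diary time S; window S−2 h to S+2 h; dose time a; trigger S−2 h ≤ a ≤ S+2 h (all Protocol 8.3.8). Look-back from the diary: 4 h (SAP 3.14.1.1).

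**1. Do the two options fit the window?**

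- Before option: the diary is at a, so between S−2 h and S+2 h. It is in window for every triggering dose.
- Delay option: the diary is at a+4 h, so between S+2 h and S+6 h. It meets the window only at a = S−2 h and is otherwise up to 4 h past its edge.

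**2. How much of the 4 h look-back does the trigger cover?** For a diary at S+k h, the look-back runs from S+k−4 h to S+k h. The part inside the trigger zone starts at S−2 h, so it lasts k+2 hours, a share of (k+2)/4.

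| Diary completed at | Share of look-back covered |
|---|---|
| S−2 h | 0% |
| S−1 h | 25% |
| S | 50% |
| S+1 h | 75% |
| S+2 h | 100% |

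For a diary at S, doses from S−4 h to S−2 h are uncovered. Four hours after such a dose is S to S+2 h, so an in-window, unaffected diary time exists, but the rule does not tell the subject to wait for it.

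**3. What happens to a delayed evening diary?** SAP 3.6 assigns diaries by calendar study day. Clock times are not given. If doses are spread evenly over the trigger span, the delay option passes midnight for none (bar the end point) when S = 18:00, 50% at 20:00, 75% at 21:00 and 100% at 22:00. The entry then counts as a third diary on the next day. SAP 3.6.1 resolves only electronic against paper entries, so no rule covers it. A Day 14 evening diary, if one is completed, would become study day 15.

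**4. How far does one score move the AUC?** Illustration on an assumed course: TSS = 15·exp(−t/4), t in days; 28 scores 12 h apart, from 0 to 13.5 days; standardized by 14/13.5 as the SAP specifies.

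| Case | AUC | Change |
|---|---|---|
| All scores on time | 60.17 | – |
| One Day 2 score 6 h late | 60.18 | +0.02% |
| That score dropped | 60.21 | +0.07% |
| That score lowered by 3 points | 58.62 | −2.6% |

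The last line follows from the trapezoid weight of one interior score: 3 × 0.5 × 14/13.5 = 1.56, and 1.56/60.17 = 2.6%. A 1-point reduction gives 0.52, or 0.9%. Such reductions add up over affected diaries. The documents give neither the size of the acetaminophen effect on TSS nor how often subjects use it.

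**The case against.** The best defence has four parts.

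- **The rule can be followed.** The before option is always in window, and the acetaminophen sentence can be read as a specific exception to the general timing. This stands in part: a reader might infer that the rule as a whole contradicts the window, and it does not. Only the delay option conflicts, and no text says that it is an exception or how such an entry is handled.
- **The primary analysis tolerates late entries.** A reader might infer that primary-endpoint scores are discarded or diaries missed. The documents do not support either. SAP 3.14.1 keeps all available scores at their actual times, exclusion occurs only in SAP 3.14.1.1, and no passage says that the eDiary closes at S+2 h.
- **A screen may be wider than an instruction.** An analyst's check over 4 h can reasonably catch residual effects of a 2 h rule. That is fair as design, but the subject rule itself uses 4 h as the waiting time. Nothing explains why a dose 3 h before the diary needs no wait.
- **SAP 3.14.1 is shorthand.** The SAP's footnote p and SAP 5.2 carry the full rule. True, but the shorthand claims that confounding is avoided, which the full rule achieves only in part.

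One further point weakens the concern. After the first diary, subjects rate the maximum since the previous one (SAP 5.2), so a recent dose need not lower the score.

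**Conclusion.** The inconsistency is real and worth correcting, but its demonstrable effect is small. The delay option falls outside the window at all but one boundary point. The trigger covers 50% of the SAP's look-back for a diary at S. A compliant dose 2 to 4 h before an on-time diary leaves a possibly affected score in the primary AUC, which only the sensitivity AUC removes. SAP 3.14.1 overstates the protection.

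These statements rest only on the documents' own times. The AUC changes rest on an assumed curve and an assumed 1- to 3-point effect. The midnight shares rest on assumed clock times.

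A reader might also infer unequal losses between arms, or a count of affected diaries from the 3000 mg/day ceiling. Neither is supported: the documents give no rate of use by arm and no dosing interval, and the ceiling permits use only for fever or pain.

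**What to change.** Change diary timing only; acetaminophen use is untouched. In Protocol 8.3.8, footnote p of both schedules and SAP 5.2:

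1. Extend the diary trigger to any dose taken or planned from 4 h before to 2 h after S. The present wording covers planned doses only.
2. For a dose 2 to 4 h before S, complete the diary 4 h after the dose. That is S to S+2 h, in window.
3. For a dose within 2 h of S, complete the diary immediately before it. That is S−2 h to S+2 h, in window.
4. Keep the 4 h delay only as a flagged fallback. It is needed when a dose after S−2 h was taken before the diary was done, because no unaffected in-window time then remains. State which day and timepoint such an entry belongs to, including after midnight.
5. Flag diaries affected by repeat doses, since a diary just before one dose can lie within 4 h of an earlier one.

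In the SAP, make 3.14.1 describe this instruction, and state in 3.14.1.1 that a diary exactly 4 h after a dose is not excluded.

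The cost is wording and a line of subject training. Dose times are already recorded, so the flags can be derived. Some diaries move by up to 2 h within the permitted window, which the AUC accommodates because it uses actual times.
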